3.1 Primary estimands

Not applicable

3.2 Secondary estimands

Not applicable

4 Study design

4.1 Overall design

Please refer to [Section 1.2 Schema](#) for study design figure.

This is a non-randomized, open-label extension study over 52 weeks with LTP001 without a control treatment arm. Participants will be presented the opportunity to consider the extension study at the End of Treatment (EOT) visit (Week 25) of the parent study CLTP001A12201. The investigator will assess if the participant will continue by verifying that the participant has completed the parent study as planned. Moreover, at the EOT the investigator will determine the eligibility for the extension study (i.e. that none of the treatment discontinuation criteria were met and that the assessments at the EOT of the parent efficacy study were completed according to the parent protocol). The patient may directly continue into the extension study. If the patient does not directly continue in the extension study, the time between the end of treatment assessments in the parent study and the enrollment in the extension study i.e. during the transition period should be kept to a minimum (it should not exceed 14 days).

Participants who are eligible and want to participate in the extension study will need to have signed an informed consent in order to receive the extension study treatment. In case of a direct transition into the extension study after the end of treatment visit in the parent study, as not all assessment results will be available (e.g. the central lab assessments) at the same day the investigator will re-assess/reconfirm the eligibility as soon as outstanding results are received.

The safety and efficacy of LTP001 will be checked at the following visits: Weeks 5, 13, 26, 39 and 52, as specified in the Assessment Schedule. Safety and tolerability assessments will take place at each visit. RHC will be performed at week 26, 6MWT and echocardiography will be assessed at Weeks 26 and 52. PAH-SYMPACT and emPHasis-10 will be collected for 7 days intervals with the seventh day of collection occurring within the allotted visit window for all Treatment visits (Weeks 5, 13, 26, 39 and 52). Participants will have safety follow-up phone calls at Weeks 9 and 17, and may be invited for safety assessment at site if deemed necessary. The PI may exercise their discretion in which safety assessments are required at these optional safety follow-up visits. Following the end of treatment period, participants will have one safety follow-up phone call approximately 30 days after the end of treatment visit at Week 52. The duration of the extension study is currently restricted to 52 weeks, but the study may be prolonged (via an amendment to the protocol) if the LTP001 development program in PAH continues and the benefit/risk assessment remains favorable for the patient population studied. The safety and efficacy profile of LTP001 that is observed in this extension study as well as the parent study, CLTP001A12201, will determine continuation of the extension study.

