This is a non-randomized, open-label extension study, over 52 weeks, with LTP001 without a control treatment arm. Participants will be presented the opportunity to consider the extension study at the End of Treatment (EOT) visit of the parent study CLTP001A12201. At the EOT visit of the parent study, the investigator will determine the eligibility for the extension study (i.e. that none of the treatment discontinuation criteria were met and that the assessments at the EOT of the parent study were completed according to the parent protocol). Participants who are eligible and want to participate in the extension study will need sign an informed consent to receive the extension study treatment. As not all assessment results will be available (e.g. lab assessments) at the same visit date, the investigator will re-assess/reconfirm the eligibility as soon as the outstanding results are received. Patients can directly transition into treatment in this extension study without un-blinding the previous treatment in the parent study. The safety and efficacy of LTP001 will be checked at the following visits: Weeks 5, 13, 26, 39, and 52, as specified in the schedule of activities. Safety and tolerability assessments will take place at each visit. 6MWT and echocardiography will be assessed at Weeks 26 and 52. RHC will be assessed at Week 26. PAH-SYMPACT and emPHasis-10 will be collected for 7 day intervals with the seventh day of collection occurring within the allotted visit window for all visits. Participants will have safety follow-up phone calls at Weeks 9 and 17, and may be invited for unscheduled assessments at the site if deemed necessary. Following the end of the treatment period, participants will have one safety follow-up phone call approximately 30 days after the end of treatment visit at Week 56.

The safety and efficacy profile of LTP001 that is observed in this extension study as well as the parent study, CLTP001A12201, will determine continuation of the extension study.

Brief Summary:

The purpose of this study is to measure the long-term safety and efficacy profile of LTP001 in participants with pulmonary arterial hypertension (PAH). The study offers participants who had completed the CLTP001A12201 double-blind parent study in PAH an opportunity to receive LTP001 (whether they were on LTP001 or not). Unblinding of the treatment received in CLTP001A12201 is not planned.

- The study duration will be up to 54 weeks.

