1.2 Schema**Figure 1-1 Study Schema****1.3 Assessment Schedule**

The Assessment Schedule lists all of the assessments when they are performed. All data obtained from these assessments must be supported in the participant's source documentation. The "X" in the table denotes the assessments to be recorded in the clinical database or received electronically from a vendor. The "S" in the table denotes the assessments that are only in the participant's source documentation and do not need to be recorded in the clinical database.

Participants should be seen for all visits/assessments as outlined in the Assessment Schedule or as close to the designated day/time as possible. Missed or rescheduled visits should not lead to automatic discontinuation.

Participants who discontinue from study treatment are to complete the end of treatment visit as soon as possible, and attend the follow-up visits as indicated in the Assessment Schedule.

Participants who discontinue from study should be scheduled for a final evaluation visit if they agree, as soon as possible, at which time all of the assessments listed for the final visit will be performed. At this final visit, all dispensed investigational product should be reconciled, and the adverse events and concomitant medications not previously reported must be recorded on the CRF.

PRO measures must be completed before any assessments are performed at any given visit.

As per [Section 4.5](#), during a public health emergency as declared by local or regional authorities (i.e. pandemic, epidemic or natural disaster that limits or prevents on-site study visits), alternative methods of providing continuing care may be implemented by the Investigator as the situation dictates. If allowable by a local health authority, national and local regulations and depending on operational capabilities, phone calls, virtual contacts (e.g. tele consultation) or visits by site staff/ off-site healthcare professional(s) staff to the participant's home, can replace certain protocol assessments, for the duration of the disruption until it is safe for the participant to visit the site again. If the Investigator delegates tasks to an off-site healthcare professional, the Investigator must ensure the individual(s) is/are qualified and appropriately trained to perform assigned duties. The Investigator must oversee their conduct and remain responsible for the evaluation of the data collected.

Table 1-2 Assessment Schedule

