Period	Baseline		Extension Treatment Up To Month 12							
Visit Name	Transition Period		Treatment						EOT	Post Study Safety Contact
Visit Numbers ¹	1 ²	100 ²	110		120		130	140	150	
Days	-14 to -1	1	29 ±7	57 ±10	85 ±10	113 ±10	176 ±10	267 ±10	358 ±10	Last treatment +30 -0 +7
Weeks	-2 to -1	1	5 ±1	9 ±2	13 ±2	17 ±2	26 ±2	39 ±2	52 ±2	57 -0 +1
Informed consent ^{3,4}	X									
Inclusion / Exclusion criteria	X									
Physical Examination			S	S ⁸	S	S ⁸	S	S	S	
Body Weight			X	X ⁸	X	X ⁸	X	X	X	
Body Temperature			X	X ⁸	X	X ⁸	X	X	X	
Blood Pressure and Pulse Rate			X	X ⁸	X	X ⁸	X	X	X	
Electrocardiogram (ECG)			X	X ⁸	X	X ⁸	X	X	X	
Dose administration ⁵	X	X	X ⁸	X	X ⁸	X	X	X	X	
Drug dispensation	X	X		X			X	X		
Collect study medication/perform drug accountability ⁵			X	X ⁸	X	X ⁸	X	X	X	
Urinalysis			X	X ⁸	X	X ⁸	X	X	X	
Pregnancy and assessments of fertility			S	S ⁸	S	S ⁸	S	S	S	
Hematology			X	X ⁸	X	X ⁸	X	X	X	
Clinical Chemistry			X	X ⁸	X	X ⁸	X	X	X	

Period	Baseline		Extension Treatment Up To Month 12								
Visit Name	Transition Period		Treatment						EOT	Post Study Safety Contact	
Visit Numbers ¹	1 ²	100 ²	110		120		130	140	150		
Days	-14 to -1	1	29 ±7	57 ±10	85 ±10	113 ±10	176 ±10	267 ±10	358 ±10	Last treatment +30 -0 +7	
Weeks	-2 to -1	1	5 ±1	9 ±2	13 ±2	17 ±2	26 ±2	39 ±2	52 ±2	57 -0 +1	
Coagulation Panel			X	X ⁸	X	X ⁸	X	X	X		
NT-proBNP				X		X		X	X		
emPHasis-10 and PAH-SYMPACT ⁶			X ⁷		X ⁷		X ⁷	X ⁷	X ⁷		
Right Heart Catheterization ⁴							X				
6-Minute Walk Test ⁴							X		X		
Echocardiogram ⁴							X		X		
Concomitant Medications/Adverse Events								X			
Study completion information									X		

Period	Baseline		Extension Treatment Up To Month 12							
Visit Name	Transition Period		Treatment					EOT	Post Study Safety Contact	
Visit Numbers ¹	1 ²	100 ²	110		120		130	140	150	
Days	-14 to -1	1	29 ±7	57 ±10	85 ±10	113 ±10	176 ±10	267 ±10	358 ±10	Last treatment +30 -0 +7
Weeks	-2 to -1	1	5 ±1	9 ±2	13 ±2	17 ±2	26 ±2	39 ±2	52 ±2	57 -0 +1
Safety Follow up Call			S		S					S

^X Assessment to be recorded in the clinical database or received electronically from a vendor

^S Assessment to be recorded in the source documentation only

¹ Visit structure given for internal programming purpose only

² Baseline and Day 1 can be on the same day or within a 14-day transition period

³ CCI

⁴ Assessment must be performed onsite. All other assessments may be performed at an off-site location.

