2.1.1 General definitions

Investigational treatment will be LTP001.

Date of first administration of study treatment (Day 1) will be defined as the date of the first actual administration of LTP001.

Date of last administration of study treatment will be defined as the date of the last actual administration of LTP001.

Two *Baselines* will be defined as the following:

Baseline of the Parent study: the Day 1 assessment of study LTP001A12201. If this datum is not available, the last pre-dosing assessment will be considered.

Baseline of the Extension study: Week 25 visit from LTP001A12201. If this datum is not available, the last pre-dosing assessment for this study (LTP001A12201E1) will be considered. *Study day* will be defined as the number of days since the date of first dose of study treatment (LTP001 or placebo). The date of first dose of study treatment will be defined as *Day 1* and the day prior to first dose of will be defined as *Day -1*. Therefore, for a particular date, study day will be calculated as follows:

for dates on or after the date of first dose of study treatment,

Study day = Assessment date – Date of first dose administration + 1

The on-treatment period lasts from the date of first administration of study treatment to the End of Study (EOS) visit or the date of last randomized dose if EOS visit is not available. The EOS visit is a follow-up visit that is approximately 30 days after the date of the last actual administration of investigational treatment. For participants who will be enrolled into the open label extension (OLE) study, their EOS visits will be skipped.

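### The extension protocol does not require a known negative pregnancy result before the first extension dose

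*Protocol*

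**What the plan says.** Entry to the extension runs through the parent study's EOT visit at Week 25. Protocol Section 4.1 allows a direct move into the extension and accepts that some results will be outstanding: "as not all assessment results will be available (e.g. the central lab assessments) at the same day the investigator will re-assess/reconfirm the eligibility" once they are received. Section 1.1 says the same ("As not all assessment results will be available (e.g. lab assessments) at the same visit date"). Table 1-2, footnote 2, fixes the timing: "Baseline and Day 1 can be on the same day or within a 14-day transition period".

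In Table 1-2 the row "Pregnancy and assessments of fertility" is empty at Visit 1 and Visit 100. Its first entry is at Day 29 ± 7 (Week 5). All its entries are coded S, defined as "Assessment to be recorded in the source documentation only".

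The other relevant provisions are:

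- Exclusion criterion 5 bars pregnant women, with pregnancy defined by a positive hCG laboratory test. Exclusion criterion 4 requires highly effective contraception.
- Section 8.4.3 says that pre-menopausal, non-sterile women will be tested, but gives no time point. Its one instruction to test first and dose only if negative concerns home urine kits in a declared public health emergency.
- Table 8-2 names a serum pregnancy test, and Section 8.4.2 sends all safety specimens to a central laboratory.
- SAP Section 2.1.1 takes the extension baseline from the parent study: "Baseline of the Extension study: Week 25 visit from LTP001A12201".

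**The concern.** Taken together, these provisions allow dosing to start while results are outstanding, schedule no pregnancy test at the start, and state no rule that a negative result must be in hand. A woman of child-bearing potential could therefore take her first extension dose before anyone knows whether she is pregnant.

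Section 2.3 states that no reproductive toxicology work has been done on LTP001 and acknowledges that treatment may carry risks to a fetus. For a woman who was on placebo in the parent study, Day 1 of the extension is her first exposure to the drug. The site cannot identify these women, because "Unblinding of the treatment received in CLTP001A12201 is not planned". Later reconfirmation of eligibility (Section 4.1) and the duty to stop treatment on pregnancy (Sections 7.1 and 8.6.4) shorten an exposure, but they act only after it has begun.

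**Working it through.** The plan gives no figure for this point. The check is a reading of the schedule and the eligibility rules, followed by day arithmetic.

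**1. Is the blank at Visits 1 and 100 real, or a broken table?** The pregnancy row has two empty cells and then seven entries. The second and fourth entries carry footnote 8, which refers to Weeks 9 and 17. That places the first entry at Week 5 (Day 29) and the two empty cells at Visits 1 and 100. The other routine safety rows start with the same two blanks, so the alignment is reliable.

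**2. Does any other provision require a known negative result?**

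| Provision | What it does | Known negative before Day 1? |
|---|---|---|
| Section 4.1, EOT check | Confirms that parent EOT assessments were done and no discontinuation criterion was met | No; results may follow |
| Exclusion 5 | Excludes on a positive hCG test | No; a pending or absent result is not a positive one |
| Exclusion 4 | Requires contraception | No; lowers the risk without verifying status |
| Section 8.1 and the Visit 1 criteria check | All criteria must be met | No; does not say which results must be in hand |
| Section 8.4.3, general rule | Testing will take place | No; no time point |
| Section 8.4.3, emergency rule | Negative home urine test before dosing | Yes, but only in a public health emergency |

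**3. How much exposure could precede a known result?** Inputs: once-daily dosing from Day 1; first scheduled extension test at Day 29 ± 7, that is Day 22 to Day 36; transition of at most 14 days (Section 4.1). On clinic days the dose is taken at the visit when staff say so (Section 6.2.3), so the test can precede that day's dose. Doses before a test on Day D are therefore D − 1.

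- **(a) Parent EOT result known before a same-day first dose:** 0 doses.
- **(b) Parent EOT sample taken, result pending for T days after a same-day first dose:** T doses. The documents give no turnaround. Assuming T = 1 to 7, this is 1 to 7 doses.
- **(c) Parent EOT result known, transition delayed the full 14 days:** the result is 14 days old at the first dose. The next scheduled test is 14 + 21 = 35 to 14 + 35 = 49 days after it. This is the interval between tests, not the duration of exposure.
- **(d) No pregnancy test at the parent EOT visit:** 22 − 1 = 21 to 36 − 1 = 35 doses before the first scheduled test; nominally 29 − 1 = 28.

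Which case applies depends on the parent schedule, which is not in these documents. About 40 participants are planned, with no split by sex or child-bearing potential, so the number of women affected cannot be estimated.

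**The case against.** The strongest reply is that this is a rollover study and the parent Week 25 visit is its baseline. Every routine safety row is blank at Visits 1 and 100 for that reason, so the empty pregnancy cell is not an oversight specific to pregnancy. The parent EOT visit may well include an hCG test, since this extension's own EOT visit does. Case (d) is therefore hypothetical.

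A second reply concerns the coding. Section 4.1 gives central laboratory results as its example of what may be pending. Hematology, chemistry, coagulation and urinalysis are coded X, which covers data received from a vendor. Pregnancy is coded S, kept in "source documentation and do not need to be recorded in the clinical database". That fits a local test read the same day, in which case nothing would be pending.

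Third, real controls exist: pregnant women are excluded, contraception is mandatory, criteria are checked at Visit 1, protocol waivers are not allowed (Section 8), and staff control the dose on clinic days. The interval in case (c) is also unremarkable beside the routine gaps of 267 − 176 = 91 and 358 − 267 = 91 days between later scheduled tests.

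Much of this stands, and it limits the size of the point. It does not remove it. A scheduled parent test is not a known result, and Section 4.1 expressly lets dosing precede outstanding results. The S code points one way, while the serum test in Table 8-2 and the central laboratory rule in Section 8.4.2 point the other. None of the controls says that a negative result must be in hand before Day 1.

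**Conclusion.** The concern holds. The extension protocol permits a same-day first dose with eligibility reconfirmed afterwards, schedules no pregnancy test before Day 29 ± 7, and does not make a known negative result a condition of the first dose outside a public health emergency.

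The possible exposure ranges from 0 doses, through 1 to 7 under an assumed laboratory turnaround, to 21 to 35 in the conditional worst case of no parent EOT test. That a result would actually be pending is an inference. Confidence is medium because the parent schedule is unseen and the documents conflict on whether the test is local or central. The change should be made: the drug has no reproductive toxicology data, the safeguard is cheap, and a first-dose check should not rest on unstated practice.

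**What to change.** Add a pregnancy-test mark at Visit 1/100 in Table 1-2 for women of child-bearing potential. State in Sections 1.1, 4.1 and 8.1 that a negative result must be known before the first extension dose. Either of two routes would satisfy the rule:

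- a same-day urine or local hCG test, with a positive result holding the dose until laboratory confirmation, so that exclusion criterion 5 keeps its wording; or
- a parent EOT result already reported and within a stated age limit.

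Section 8.4.3 already contains a negative-before-dosing rule for emergencies, which can be extended to Day 1. If the parent protocol already requires a reported negative result at EOT, one cross-reference to it is enough.

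The cost is one table mark, two or three sentences, and one simple test per woman of child-bearing potential. The downside is a short dosing delay if that test is positive or if only a central result is accepted. Because parent treatment stays blinded, such a delay could not be confined to former placebo participants. Women who test negative on the same day have no gap in treatment.

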4.1.1 Off-site procedures

At the investigator's direction and based on benefit-risk considerations of the participant's clinical condition, qualifying participants may be offered the option to have certain clinical trial procedures performed, not mandated to be performed onsite, at an off-site location, as defined in [Table 1-1](#). A hybrid model is planned for this study incorporating both onsite and off-site visits. The off-site procedures will be utilized in certain countries and sites as determined by protocol needs and based on national and local/site regulations. Participants have the option of

participating in one or more off-site visits, based on their preference and the investigator's discretion.

One or more of the following elements may be implemented to support off-site visits where allowed by national and local regulations:

- Telemedicine
- Off-site Healthcare Professionals (OHP)
- Direct-to-participant shipment of study supplies
- Direct-to-participant shipment of study treatment (refer to [Section 6](#))
- Electronic Source (eSource) Direct Data Capture (DDC)

4.1.1.1 Responsibility of Investigators

Procedures that are performed off-site remain under the oversight of the investigator, who retains accountability for the conduct of all safety and efficacy assessments delegated to an OHP, and will ensure the rights, safety and wellbeing of participants. This includes the following, but is not limited to:

- the identification, management and reporting of AEs and SAEs are performed in accordance with the protocol and applicable regulations including the review of PROs to identify any unreported AEs or SAEs.
- OHPs have appropriate qualifications, training, and experience to successfully conduct off-site procedures
- source data collected off-site are reviewed and evaluated in a timely manner
- the investigator or delegate is available to be contacted by the OHP if any issues or concerns are noted during an off-site visit
- where relevant, the investigator or delegate will be present via telemedicine for a portion of the off-site visit to support the physical examination

4.1.1.2 Responsibility of Off-site Healthcare Professionals

OHPs must have the required qualifications, training, and experience to conduct off-site assessments. OHPs are responsible to conduct delegated assessments and collect relevant data at off-site visits in accordance with the clinical trial protocol, International Conference for Harmonization (ICH) Good Clinical Practice (GCP) guidelines, and national and local regulations and guidelines.

During an off-site visit, the OHP will conduct drug accountability and send IMP back to the investigational site for review by the field monitor.

The OHPs will be provided by a third-party vendor sourced by Novartis. Where a site wishes to use OHPs that are not provided by Novartis this must be agreed with Novartis before use.

Any issues or safety concerns identified by the OHP will be promptly communicated to the investigator or delegate according to a pre-defined communication plan.

4.1.1.3 Telemedicine

The sponsor has qualified and contracted a third-party vendor to provide a telemedicine platform technology for this study. The selected platform is a validated system complying with relevant ICH E6 GCP guidelines. Trial participants can interact with site personnel using online communication tools built into the platform, enabling the following capabilities:

- Secure videoconferencing which allows the participant, OHP and site personnel to be connected
- Reminders to be automatically sent to participants (e.g. visit or dosing reminders)
- eSource Direct Data Capture (DDC) (see [Section 10.1.5.1](#))

